Participants were randomized 1:1 to the consumer health informatics smartphone-based intervention app or a control app with only data collection. Permuted block randomization (pairs) was performed using a computer-generated code within a secure central online data management system, Research Electronic Data Capture (REDCap), which was used to store and manage all participant data. No randomization was instituted for the clinician-facing intervention; instead, the decision support tool was embedded into the electronic health record to facilitate optimized opioid prescription upon discharge based on recorded inpatient use. This was implemented after half of the participants were enrolled. The principal investigator, coinvestigators, clinical coordinating center staff, participants, and statisticians remained masked to treatment assignment until the database was locked for analysis.

Sample Size Justification

To estimate power and sample size for the primary outcome, self-reported cumulative opioid use in the four weeks after discharge, investigators combined data from previous observational studies on opiates taken at one week from discharge, where variability in opioid consumption is greatest, and summed across four weeks from discharge and then log-transformed values appropriately. Investigators utilized SAS Proc Power (version 15.2, SAS Institute Inc., Cary, NC, USA) software and specified significance level alpha = 0.05 two-tailed. Across decision support tool activation status and surgical subspecialties, 300 participants per app group provided 85% power to detect minimum effect sizes (ES) of 0.23 in opioids consumed at one week and of 0.245 in opioids consumed across four weeks. Data was similarly

combined for pain intensity scores from prior studies and could detect a minimum effect size of 0.244 in pain intensity t-score at week one following discharge. Within decision support tool type and across specialty (i.e., the three-way interaction among app, decision support tool, and time), 150 participants per group provided 85% power to detect minimum effect sizes of 0.35 in opioids consumed at one week, 0.35 in opioids consumed across four weeks, and 0.35 in pain intensity t-score at one week after discharge.

Procedures

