Investigators primarily tested a participant-facing app to reduce opioid intake which was designed and implemented through a user-centered design approach. The intervention app provided education on elements of pain management that could be modified by patients, including: 1) post-operative pain expectations, 2) pharmacologic alternatives to opioids, 3) opioid safety and appropriate disposal, and 4) non-pharmacological therapy, such as meditation. The control app featured the same interface but only collected patient data. The app was deployed to research team members and pilot participants for beta testing before finalization.

Baseline information was obtained from the participant in-person during the index hospitalization. During this visit, patients familiarized themselves with the format, asked questions, and received explanations regarding the apps' functionality. Following discharge, a weekly notification was sent to the participant, reminding them to complete standardized surveys and custom questionnaires during the first four weeks following discharge, a time when most opioids are consumed and when patients have shown to report consumption accurately. The day of discharge was considered day 0. If no responses were obtained via the app, participants were followed up by telephone.

In addition to the participant-facing app intervention, a clinician-facing decision support tool was operationalized for the second half of the study period for participants not requiring opioids 24 hours prior to discharge. Previous work in three diverse samples of surgical procedures found that among available predictor variables that could be incorporated into an electronic decision support tool, 24-hour pre-discharge opioid intake was most strongly associated with patient-reported post-discharge opioid intake.

Outcomes

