The primary outcome was self-reported cumulative oral morphine milligram equivalents (MME) in the first four weeks after discharge. The secondary outcomes were amount of opioid prescription at discharge, supplementary opioid prescriptions within four weeks after discharge, disposal of leftover opioids within four weeks of discharge, pain intensity scores during the four weeks after discharge, and pain interference scores during the four weeks after discharge. Non-opioid prescriptions within four weeks of discharge were an exploratory outcome. Pain intensity and interference were both quantified using the National Institutes of Health Patient-Reported Outcomes Measurement Information System (PROMIS®) four-item pain intensity scale at four weeks and the four-item scale pain interference score at four weeks. All PROMIS™ scores were analyzed as standardized T-scores (mean 50, standard deviation 10).

Independent variables included sociodemographic characteristics obtained from the electronic health record and from a questionnaire provided to participants during their hospitalization: age, sex, race, ethnicity, body mass index (kg m²-1), and insurance type. Health history variables were obtained via surveys and electronic health records as necessary and included history of substance use disorder, PROMIS™ Sleep Disturbance Score, Patient Health Questionnaire-(PHQ-8) score, pre-operative opioid use, preoperative benzodiazepine use, preoperative gabapentinoid use, and preoperative antidepressant use. Clinical characteristics included the primary surgical subspecialty for the requisite hospital stay, multiple procedures performed during admission, total in-hospital opioid intake, pain score at discharge, and length of hospital stay.

Adverse events were monitored. For this study, an adverse event was considered as one requiring more than two additional opioid prescriptions within two weeks of discharge and/or access of confidential information by a non-authorized person. We considered a serious adverse event as all-cause mortality and/or re-hospitalization for any reason.

Statistical analysis

Baseline balance on potential confounding characteristics was assessed using absolute standardized difference (ASD), calculated as the difference in means or proportions divided by the pooled standard deviation. A variable was considered imbalanced if the ASD was greater than 0.16.

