For the primary analysis, the effect of the intervention app on self-reported cumulative opioid use in the four weeks after discharge was modeled by log-transforming the outcome variable and then fitting a linear regression model with the app treatment group as the covariate. The treatment effects were estimated as ratio of geometric means. A sensitivity analysis was conducted using quantile regression to test the robustness of results to outliers. A model was fit with an interaction between app and decision support tool groups to evaluate potential multiplicative effects between the groups. Analysis was on a modified intention-to-treat basis, excluding participants that did not engage with the intervention or answer survey questions. There were no partial responses to the opioid-related outcomes. Missing data from pain-related survey responses were imputed from the mixed effects model.

For the secondary analysis, the effect of the intervention app on opioids prescribed at discharge was modeled by log-transforming the outcome and fitting a linear regression model with the app treatment group as the covariate. The effect of the intervention app on supplementary opioid requirements in the four weeks after discharge, opioid disposal, and non- opioid prescriptions in the four weeks after discharge was evaluated using a logistic regression model. The effect of the app on pain intensity and interference t-scores was evaluated by fitting linear mixed models with fixed covariates for app treatment group and time (categorical), and random effects for participant identification code. No interim analyses were planned because the population studied was not considered high risk for adverse events, the interventions were generally considered not harmful and to prevent alpha dilution.

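### The 0.35 SD power figure is labelled a three-way interaction that no planned model fits, and pain-intensity power is stated for week one although the pain model gives one pooled app effect

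*Combined protocol and SAP*

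**What the plan says.** **Power (Sample Size Justification).** With 300 per app group, two-sided alpha 0.05 and 85% power, the trial "could detect a minimum effect size of 0.244 in pain intensity t-score at week one following discharge". A second statement, for 150 per group, opens by describing comparisons inside a decision support tool type. In parentheses it then calls them "the three-way interaction among app, decision support tool, and time". The detectable effects listed are "minimum effect sizes of 0.35 in opioids consumed at one week, 0.35 in opioids consumed across four weeks, and 0.35 in pain intensity t-score", the last again at one week.

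**Outcomes.** The secondary outcomes are listed as "pain intensity scores during the four weeks after discharge, and pain interference scores during the four weeks after discharge". A later sentence in the same section describes the measures as the "four-item pain intensity scale at four weeks and the four-item scale pain interference score at four weeks".

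**Data collection (Procedures).** Over the first four weeks "a weekly notification was sent to the participant, reminding them to complete standardized surveys".

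**Analysis (Statistical analysis).** Pain intensity and interference are each analysed by "fitting linear mixed models with fixed covariates for app treatment group and time (categorical), and random effects for participant identification code". The only interaction named is in the paragraph on the primary outcome: "A model was fit with an interaction between app and decision support tool groups". It has no time component.

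**The concern.** There are two mismatches between what is powered and what is fitted.

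1. **The 0.35 figure.** It is presented as power for a three-way interaction. No model in the Statistical analysis section contains app by tool by time. The same sentence applies the label to opioids totalled over four weeks, which is one number per participant and cannot interact with time. Power for an interaction with time would also need a within-person correlation, and none is given. A reader could conclude that the trial had 85% power to show that the app effect depends on the tool. It does not have that at 0.35 SD.

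2. **Pain intensity.** Power is stated for a difference at week one. A model with app and categorical time as main effects only has a single app coefficient, so it reports neither a week-one nor a week-four difference. The stated power therefore belongs to a contrast that the planned analysis does not produce. A small pooled effect could be misread as ruling out the week-one difference that the trial says it could detect. The two timings in the Outcomes section leave the intended pain effect open as well.

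**Working it through.** **Inputs from the document.** Two-sided alpha 0.05; 85% power; 300 per app group; 150 per group within tool type; effect sizes 0.244 and 0.35 in SD units; weekly surveys for four weeks. The tool was switched on after half of enrolment, so app by tool gives four cells of 150.

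**Assumptions, not in the document.** Unit variance; four complete weekly scores; equal within-person correlation ρ = 0.3 / 0.5 / 0.7 (triplets below follow that order). Normal approximation, with z(0.975) + z(0.85) = 1.960 + 1.036 = 2.996.

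**Step 1. Reproduce the stated figures as two-group contrasts at one time point**, SE = √(2/n).
- n = 300: SE = 0.0816. Detectable effect 2.996 × 0.0816 = 0.245; power at 0.244 is 84.8%.
- n = 150: SE = 0.1155. Detectable effect 2.996 × 0.1155 = 0.346; power at 0.35 is 85.8%.

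Both reproduce. The 0.35 is the app effect within one tool type, not an interaction of any order.

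**Step 2. Power for real interactions at 0.35 SD.**
- App by tool, one value per participant: SE = √(4/150) = 0.1633. Power is 57%; 85% needs 2.996 × 0.1633 = 0.489 SD.
- App by tool by time, taken as week one minus week four: SE = √(8(1−ρ)/150) = 0.193 / 0.163 / 0.126. Power is 44% / 57% / 79%. No such analysis is planned; this only shows that the label does not fit the number.

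**Step 3. Power of the pooled pain effect.** With complete data the app coefficient is the mean of the four weekly differences. The variance of a participant's four-week mean is (1+3ρ)/4, so with 300 per arm SE = √[((1+3ρ)/4)(2/300)] = 0.0563 / 0.0645 / 0.0719. For 85% power the average effect must be 0.169 / 0.193 / 0.215 SD, which is 69% / 79% / 88% of 0.244.

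| Effect over weeks 1 to 4 (week one = 0.244 SD) | Average (SD) | Power at ρ = 0.3 / 0.5 / 0.7 |
|---|---|---|
| Constant | 0.244 | 99% / 97% / 92% |
| Linear fade to 70% of week one | 0.207 | 96% / 89% / 82% |
| Linear fade to 40% of week one | 0.171 | 86% / 75% / 66% |
| 0.244, 0.122, 0.061, 0 | 0.107 | 47% / 38% / 32% |
| Week one only | 0.061 | 19% / 16% / 14% |

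**Step 4. Cost in precision of weekly contrasts.** SE 0.0816 against 0.0563 / 0.0645 / 0.0719 is 45% / 26% / 14% larger. The 95% half-width is 0.16 SD, against 0.11 to 0.14 SD for the average.

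**The case against.** The strongest defence is that nothing in the pain analysis is invalid. The pooled effect is a legitimate target for pain over the four weeks, as the secondary outcomes are listed, and adding app by time would not change it with complete data. Under a constant effect the planned test has more power than claimed. The three-way label is a faulty parenthesis in a sentence that opens with the correct description, and the Statistical analysis section promises no three-way test. The past-tense text, including the remark that the opioid outcomes had no partial responses, suggests that data have been seen, so new weekly contrasts would be post hoc.

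Most of this stands. It is why the power text should be corrected first and the model term should be supportive. It does not rescue the label: 85% power is claimed for a term that no model fits, and the interaction that is fitted has 57% at that effect size.

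A reader might infer that the pain analysis is underpowered. The documents do not support that, because they give neither a time course nor a correlation, and Step 3 runs in both directions. A reader might also extend the mismatch to pain interference. That outcome shares the model, but no power is stated for it.

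**Conclusion.** The point holds as two errors in the stated power.

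- **Interaction.** The 0.35 SD at 85% is a within-tool-type app contrast. The fitted app-by-tool interaction has 57% power at 0.35 SD and needs 0.49 SD for 85%. This rests only on four cells of 150 and needs no assumed correlation. It bears on the interaction model in the primary-analysis paragraph.
- **Pain intensity.** The stated power is for week one, and the model reports a pooled effect. Under the assumptions above, 85% power needs an average of 0.169 to 0.215 SD. A constant or mildly fading effect generally keeps about the stated power or better; a marked fade loses it.

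Calling the pooled effect a four-week average assumes complete weekly scores and no discharge-day score among the time levels, which the text does not settle.

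It would go too far to say that the trial's sample size is wrong. The primary app main-effect comparison does not depend on either statement.

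**What to change.** 1. **Sample Size Justification.** Describe 0.35 as the app contrast within one tool type and delete the three-way label. Add that app by tool has 57% power at 0.35 SD and needs 0.49 SD for 85%.
2. **Pain estimand.** Name the four-week average app effect. Restate pain-intensity power for it (0.17 to 0.22 SD at 85%, with the correlation assumption shown), and reconcile the two timings in the Outcomes section.
3. **Supportive addition.** Include app by categorical time in the pain models. Report the week-one and week-four contrasts beside the average, with confidence intervals and not as extra tests. Label them post hoc if data have been seen.

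Items 1 and 2 cost only wording. Item 3 is one model term on scores already collected. In a single check fit by restricted maximum likelihood, the average was the same with and without the term (0.055, standard error 0.062). The downside is that weekly contrasts have standard errors 14% to 45% larger than the average, and three estimates on each of two scales make six secondary estimates.

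### The two pain models use no baseline pain score, and no baseline PROMIS pain scale is listed, so the app comparison on pain is valid but less precise than it could be.

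*Combined protocol and SAP*

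**What the plan says.** All references are to the combined protocol and SAP.

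- **Statistical analysis**, secondary analysis: the pain intensity and interference T-scores are analysed by "fitting linear mixed models with fixed covariates for app treatment group and time (categorical), and random effects for participant identification code". No other term is named.
- **Procedures**: "Baseline information was obtained from the participant in-person during the index hospitalization". The section does not itemise that information. Survey reminders then follow weekly for four weeks after discharge.
- **Outcomes**: the two four-item PROMIS pain scales appear only as post-discharge outcomes. PROMIS Sleep Disturbance and PHQ-8 are among the health-history variables, whose sources are given as surveys and health records without a stated visit. The clinical characteristics include "total in-hospital opioid intake, pain score at discharge, and length of hospital stay". The instrument for the discharge pain score is not named, nor is its timing relative to allocation.
- **Randomization and masking**: "Participants were randomized 1:1 to the consumer health informatics smartphone-based intervention app". The moment of randomization relative to the in-hospital visit is not stated.
- **Sample Size Justification**: the pain data "could detect a minimum effect size of 0.244 in pain intensity t-score at week one following discharge".

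**The concern.** Pain intensity and pain interference are two of the five secondary outcomes. People differ widely in pain after surgery, and part of that difference is usually visible before follow-up starts. If it is measured before allocation and put in the model, it leaves the error variance of the app comparison. If not, it stays there.

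The participant random effect does not do this job. It describes the correlation among one person's weekly scores, but each person is in one app group throughout, so between-participant variance still feeds in full into the standard error of the app effect. Only a covariate that predicts a participant's level of pain can reduce it.

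At stake is the width of the confidence intervals for the two pain contrasts. A model with a baseline score would also take account of chance imbalance in that score. The planned balance check, which flags standardized differences above 0.16, is descriptive and leads to no stated adjustment of the pain models.

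**Working it through.** **Inputs from the documents**

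- Significance level: "specified significance level alpha = 0.05 two-tailed".
- Sample size and power: the pain sentence repeats neither, so both are carried over from the sentence before it, "300 participants per app group provided 85% power to detect minimum effect sizes (ES) of 0.23 in opioids consumed at one week". Only the 300 per group and the 85% are used here.
- Detectable pain intensity difference at week 1: 0.244 standard deviations. On the T-score metric (SD 10) this is 2.44 points. The trial's own SD is not given.

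**Assumed inputs, not in the documents**

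- r, the correlation between an in-hospital baseline T-score and a post-discharge T-score: 0.2 to 0.5.
- ρ, the correlation between any two follow-up weeks: 0.6. It is used only in step 3.

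**Step 1: reproduce the plan's figure.** For an unadjusted comparison of two means at one time point, the detectable difference is (1.960 + 1.036) × √(2/300) = 0.2447, against 0.244 stated. Power at 0.244 is Φ(0.244 × √(300/2) − 1.960) = Φ(1.028) = 84.8%, and 85% power needs 302 per group. With 150 per group the same formula gives 0.346, in line with the stated "0.35 in pain intensity t-score at one week after discharge". The figures therefore match an analysis with no baseline adjustment.

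**Step 2: add a baseline covariate, week 1.** The residual SD is multiplied by √(1 − r²). The detectable difference is 0.244 × √(1 − r²), power at 0.244 is Φ(2.988/√(1 − r²) − 1.960), and the equivalent unadjusted sample size is 300/(1 − r²).

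| r (assumed) | √(1 − r²) | SE falls by | Detectable difference (SD) | T-score points | Power at 0.244 | Equivalent n per group |
|---|---|---|---|---|---|---|
| 0.2 | 0.980 | 2% | 0.239 | 2.39 | 86.2% | about 312 |
| 0.3 | 0.954 | 5% | 0.233 | 2.33 | 88.0% | 330 |
| 0.4 | 0.917 | 8% | 0.224 | 2.24 | 90.3% | 357 |
| 0.5 | 0.866 | 13% | 0.211 | 2.11 | 93.2% | 400 |

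**Step 3: the four-week model.** The stated model has no app-by-time term, so its app effect is an average over time. For four weekly scores with equal correlation ρ, the variance of a participant's mean is (1 + 3ρ)/4, which is 0.70 at ρ = 0.6. Baseline adjustment lowers it to 0.70 − r²:

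- r = 0.2: 0.66, a variance reduction of 6%
- r = 0.3: 0.61, a reduction of 13%
- r = 0.5: 0.45, a reduction of 36%

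The week-1 variance reductions (r²) at the same r are 4%, 9% and 25%. If r holds across all four weeks, the week-1 table is on the low side for the planned model.

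**Step 4: pain interference.** The documents give no power or detectable difference for it. The factor √(1 − r²) applies with its own r, but there is no stated figure to move.

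**The case against.** The strongest reply is that nothing here is invalid. Randomization makes the unadjusted contrast a legitimate estimate, its stated power reproduces without help from a covariate, and the primary model is unadjusted as well. The gain is modest: in T-score points, 0.05 at r = 0.2 (2.44 − 2.39) and 0.33 at r = 0.5 (2.44 − 2.11). Pain in hospital, under inpatient analgesia and across mixed specialties, may predict pain at home only weakly. All of this stands, and it limits the point to precision. The exclusion of non-engaging participants after randomization is a separate matter on which this point does not rest.

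Several stronger readings are tempting but unsupported:

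- *Baseline pain was not measured.* A reader might infer this from the lists, but they are introduced as inclusions and the baseline visit is not itemised. The documents support only that neither pain scale is listed.
- *The in-hospital questionnaire already holds PHQ-8 and Sleep Disturbance, so pain was overlooked on the same form.* The Outcomes section links that questionnaire to the sociodemographic variables and does not say when the other two were completed.
- *The discharge pain score is contaminated by the app.* Participants were shown the apps in hospital, so this is possible. But no section orders allocation and the discharge score, or says that educational content was delivered before discharge.
- *Imbalance in starting pain cannot be corrected.* A discharge pain score is collected. If it precedes allocation, it can be used.
- *The trial must show that pain did not worsen.* This is a natural clinical reading of an app meant to reduce opioid intake, but the documents state no non-inferiority aim or margin for pain.

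Finally, the text is in the past tense. New baseline items may be out of reach, which leaves only the analysis part of the fix.

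**Conclusion.** The point holds as a missed gain in precision, not as a flaw in validity. As written, both pain models omit any baseline pain term, no baseline PROMIS pain scale is listed, and an in-person visit offered an occasion to collect one. The direction is secure for any appreciable correlation. The size rests wholly on an assumed r: from a negligible 2% of the week-1 standard error at r = 0.2 to 13% at r = 0.5, the latter equal to 100 more participants per group (400 − 300). These figures are for pain intensity. For interference only the direction can be stated.

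**What to change.** 1. **Procedures and Outcomes:** give the four-item PROMIS pain intensity and four-item pain interference scales at the in-hospital visit, before allocation, in both arms, and list them among the baseline variables. State when randomization takes place relative to that visit.
2. **Statistical analysis:** add the matching baseline T-score as a fixed covariate in each pain model.
3. **If collection is complete:** adjust the pain models for prognostic variables already recorded before allocation, for example age, surgical subspecialty and preoperative opioid use, and fix the list before treatment groups are unmasked. State when and on what instrument the discharge pain score was taken. Use it in the main model only if it was recorded before allocation. Otherwise confine it to a supportive model and say that the app may have affected it.

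The cost is eight self-report items at an existing visit, a few minutes per participant, and one extra term per model. The third step needs no new data.
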